# 6.3.7. COVID-19 Related Endpoint 3 - Effectiveness of 13vPnC against severe COVID-19 disease

VE will be calculated as 1 minus the odds ratio for PCV13 vaccination among cases and controls, multiplied by 100, overall and among immunocompetent persons only.

## 6.3.7.1. COVID-19 Related Endpoint 3 - Main Analysis

In this analysis:

- The cases are CAP cases with COVID-19 with severe clinical outcomes
- The controls are CAP cases with COVID-19 without severe clinical outcomes

The controls will be selected by matching by the propensity score as described above. We will then develop six models as follows:

Model 1: Cases: COVID-19+ve with any severe outcome; Controls: COVID-19+ve without a severe outcome

Model 2: Cases: COVID-19+ve and admitted to ICU; Controls: COVID-19+ve and not admitted to ICU

Model 3 : Cases: COVID-19+ve and PaO2/FiO2 ratio <250 mmHg; Controls: COVID-19+ve and PaO2/FiO2 ratio ≥250 mmHg

Model 4: Cases: COVID-19+ve and Respiratory rate >30 breaths/min; Controls: COVID-19+ve and Respiratory rate ≤30 breaths/min

Model 5: Cases: COVID-19+ve and died; Controls: COVID-19+ve and alive.

DMB02-GSOP-RF02 5.0 Statistical Analysis Plan Template 05-Dec-2019
PFIZER CONFIDENTIAL
Page 40
TMF Doc ID: 98.03

Model 6: Cases: COVID-19+ve and received mechanical ventilation; Controls: COVID-19+ve and did not receive mechanical ventilation

Model 7: Cases: COVID-19+ve and diagnosed as ARDS; Controls: COVID-19+ve and not diagnosed as ARDS

For each of the models, we will employ a conditional logistic regression model and will estimate odds of exposure to PCV13 among cases versus controls. The VE estimate will be calculated as (1 – odds ratio) × 100%. We will use a two-sided alpha of 0.05 for all analyses.

These models will also be replicated for immunocompetent (absence of immunocompromising conditions, i.e., high-risk conditions) persons only.

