 - COVID-19 vaccination, dates and vaccines types.
 - RSV vaccination, dates and vaccine types.
- Hospitalisation data:
 - Dates and time of admission/discharge for qualifying admission.
 - ICU stay (yes/no).
 - Number of days in ICU.
 - Mechanical ventilatory support (invasive and non-invasive), if used and type.
 - Number of days of mechanical ventilator use.
 - Acute respiratory distress syndrome (ARDS) diagnosis during illness.

PFIZER CONFIDENTIAL CT45-GSOP-RF152.0 Low-Interventional Study Protocol Template 05-Dec-2019 Page 36 of 70

- Readmission within 14 days of discharge (If yes, dates of admission/discharge).
- Symptoms of qualifying pneumonia illness mentioned in inclusion criteria.
- Date of illness onset.
- Vital signs (initial respiratory rate, pulse oximetry, blood pressure, heart rate).
- Level of oxygen supplementation during pulse oximetry measurement (FiO2).
- SOC chest radiography results (eg, CXR and computed tomography [CT] scan), including if consistent with pneumonia per standard outlined in Section 11.3.
- SOC microbiology test results including test and specimen type:
 - Blood cultures.
 - Respiratory microbiology testing, including bacterial (eg, PCR and culture), viral testing (eg, RSV, influenza, and COVID-19), and Gram stain results.
 - All standard –of care COVID-19 testing during the qualifying illness will be recorded with result.
 - Pneumococcal testing (eg, *BinaxNOW*[®] or another pneumococcal antigen urine test).
 - Other body fluid/tissue sterile under normal conditions.
- CAP severity/prognosis scale (Confusion Respiratory Rate Blood Pressure [CRB-65] and Pneumonia Severity Index [PSI]) on presentation to hospital if information available from SOC testing to calculate score:
 - CRB-65 score [Contributing data elements: age, blood pressure, presence of confusion, and respiratory rate].
 - PSI score. Contributing data elements are:
 - Altered mental status.
 - Nursing home residency.
 - pH and partial pressure of arterial O2 (PaO2) from atrial blood or arterialised venous blood OR oxygen saturation level (SpO2) measured by pulse oximetry

PFIZER CONFIDENTIAL CT45-GSOP-RF152.0 Low-Interventional Study Protocol Template 05-Dec-2019 Page 37 of 70

and FiO2 during that assessment.

- Blood urea nitrogen.
- Serum sodium concentration.
- Plasma glucose concentration.
- Hematocrit.
- Presence of pleural effusion.
- Relevant medical history:
 - COPD.
 - Asthma.
 - Congestive Heart Failure.
 - Coronary Artery Disease (CAD).

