#### Selection of controls using propensity score matching

In the 1st sensitivity analysis, the cases will be the patients with CAP in whom PCV13 serotypes are identified by any method and the controls will be the patients with CAP without having VT serotype (even the CAPs for which the serotype was not identified). The controls will be selected using propensity score matching. A propensity score is the conditional probability of assignment to a treatment given a vector of covariates including the values of all treatment confounders (vida infra). We will select the required number of controls matching by the propensity score of the case. Several types of propensity score matching are available in literature. We will use nearest neighbor matching (without replacement, meaning a control cannot be the control of any other case) within a specified caliper distance (Rosenbaum & Rubin, 1985). The caliper distance will be set to 0.2 of propensity score (i.e., 0.2 standard deviations of whatever distance will be measured), so that matching controls remain within the specified distance of the propensity score. Note that 0.2 of the pooled standard deviation of the logit of the propensity score will eliminate approximately 99% of the bias due to the measured confounders (Austin 2011). The maximum number of controls for a case will be determined based on the exact case-control ratio in the data. If less than the maximum number of controls exists within the set caliper distance of 0.2, then only those controls within the caliper distance will be selected and that case will have less than the maximum number of controls.

DMB02-GSOP-RF02 5.0 Statistical Analysis Plan Template 05-Dec-2019
PFIZER CONFIDENTIAL
Page 32
TMF Doc ID: 98.03

We may also perform a sensitivity analysis by selecting controls setting the caliper distance to 0.1 of the propensity score.

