## Variables to be used to calculate the propensity scores

Variables for calculating the propensity score.

- Patients' age: continuous
- Sex: female=0, male=1
- Nationality: Spanish=0, non-Spanish=1
- Risk level: low-risk=0, at-risk=1, high-risk=2
- PSI score: continuous
- Antibiotic use within past 14 days: no=0, yes=1)
- Influenza vaccination within past one year: yes=0, no=1
- Pneumonia in the last year: ordinal value=0, 1,2,3
- Season of admission: Spring (Mar-May)=0, Summer (Jun-Aug)=1, Autumn (sep-Nov)=2, Winter (Dec-Feb)=3.
- PPV23 receipt in past 5 years: yes=0, no=1
- CAP event occurrence during COVID-19 pandemic: 0=not during COVID-19, 1=During COVID-19 (The study is started in the pandemic period; the variable will be used if we find a non-pandemic period during the study period)

The study site will be exactly matched. Note that the categorical variable will be put in the model like the ordinal values.

The conditional logistic regression will be employed to estimate odds of exposure to PCV13 among these matched cases and controls. The VE estimate will be calculated as  $(1 - \text{odds ratio}) \times 100\%$ . We will use a two-sided alpha of 0.05 for all analyses.

In the 2nd sensitivity analysis (PPV23 Naïve population), the cases will be the hospitalized CAP in whom PCV13 serotypes are identified by any method and had not received PPV23 in the last five years from the date of visit; the controls (also PPV23 Naïve population), will be selected using the propensity score matching as described above. A conditional logistic regression will be employed to estimate odds of exposure to PCV13 among cases versus controls in the PPV23 naïve population. The VE estimate will be calculated as (1 – odds ratio) × 100%. We will use a two-sided alpha of 0.05 for all analyses.

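### Matching on PSI in the analysis of PCV13 effectiveness against severe COVID-19 adjusts for a post-vaccination measure of severity and can attenuate the VE

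*SAP*

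**What the plan says.** SAP 6.3.7.1 compares COVID-19-positive CAP patients with and without a severe outcome. The text announces six models but lists seven, numbered here as listed: any severe outcome (1), ICU admission (2), PaO2/FiO2 below 250 (3), respiratory rate above 30 (4), death (5), mechanical ventilation (6) and ARDS (7). On control selection it says "The controls will be selected by matching by the propensity score as described above" and gives no covariate list of its own.

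The only score described earlier is in SAP 6.1.1.2. Its list contains "PSI score: continuous", along with "Patients' age: continuous", sex, nationality, risk level, recent antibiotics, influenza vaccination, pneumonia in the last year, season, PPV23 receipt and a pandemic-period indicator. Also, "The study site will be exactly matched". Nothing removes PSI for the COVID-19 models.

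Protocol 10.3 places PSI at presentation to hospital. Its listed inputs include altered mental status, urea, and either PaO2 or "oxygen saturation level (SpO2) measured by pulse oximetry" together with FiO2. SAP 3.4 (Oxygenation Parameters) derives PaO2 from SpO2, and the case definition of Model 3 is "Cases: COVID-19+ve and PaO2/FiO2 ratio <250 mmHg". SAP 3.3.2 states that this VE is to be adjusted for confounders.

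**The concern.** A confounder of the effect of PCV13 on COVID-19 severity has to precede or be independent of that effect. PSI is recorded after vaccination, during the illness whose severity is the outcome. If PCV13 lowers severity at admission, it lowers PSI too. Comparing cases with controls of similar PSI then holds constant part of what the vaccine is supposed to change. The estimate drifts from a total effect towards the part that does not pass through admission severity, and a weak result would be harder to read.

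**Working it through.** **Where PSI overlaps each outcome**

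| Model | Outcome | Relation to PSI in the visible documents |
|---|---|---|
| 3 | PaO2/FiO2 below 250 | Shared measurement (oxygenation) |
| 1 | Any severe outcome | Shared through the PaO2/FiO2 limb |
| 2, 5, 6, 7 | ICU, death, ventilation, ARDS | Not inputs; later results of the severity PSI grades |
| 4 | Respiratory rate above 30 | Listed in Protocol 10.3 under CRB-65, not under PSI; the PSI table in SAP Appendix 2.3 is not visible, so overlap is unconfirmed |

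**Why a vaccination model still lets PSI in.** The SAP defines the score by treatment: "A propensity score is the conditional probability of assignment to a treatment given a vector of covariates". Write it as logit P(PCV13) = a + b·X + g·PSI, with X the other covariates. If PCV13 has no effect on severity and X captures confounding, g is near zero and PSI drops out. If PCV13 lowers admission severity, vaccinated patients have lower PSI at given X, g is non-zero, and matching on the score partly balances PSI. PSI therefore gains weight when there is an effect to remove.

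**Size.** The documents give no expected VE, sample size or power for this endpoint, so there is no plan figure to reproduce. Two simulations were run on assumed inputs. Share of VE lost = (VE without PSI − VE with PSI) / VE without PSI.

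*Simulation A: large-sample stratification.* 600,000 subjects; score from age, risk level and influenza vaccination, with or without PSI; Mantel-Haenszel OR over 200 propensity strata. Assumed: PCV13 lowers latent severity by 0.25 SD, and severe means the worst 25%.

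| Correlation of PSI with severity | VE without PSI | VE with PSI | Share lost |
|---|---|---|---|
| 0.5 | 33.2% | 25.0% | 8.2/33.2 = 25% |
| 0.6 | 33.8% | 22.5% | 11.3/33.8 = 33% |
| 0.7 | 33.6% | 18.1% | 15.5/33.6 = 46% |
| 0.8 | 34.1% | 13.3% | 20.8/34.1 = 61% |

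*Simulation B: matching as in the SAP.* 12 replicates of 8,000 COVID-19-positive patients; site matched exactly; nearest neighbour without replacement; conditional logistic regression. The SAP says "The caliper distance will be set to 0.2 of propensity score" and then refers to standard deviations; 0.2 SD of the logit was used. Up to 4 controls per case were taken (an assumption; the SAP ties the maximum to the observed ratio). PSI was assumed to contain oxygenation but not respiratory rate, the vaccine to act through admission severity, and age, sex and risk level to capture confounding.

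| Outcome | Moderate effect: without → with PSI | Share lost | Stronger effect: without → with PSI | Share lost |
|---|---|---|---|---|
| PaO2/FiO2 below 250 | 41% → 24% | 17/41 = 41% | 58% → 35% | 23/58 = 40% |
| Any severe outcome | 35% → 22% | 13/35 = 37% | 51% → 31% | 20/51 = 39% |
| ICU admission | 30% → 20% | 10/30 = 33% | 41% → 25% | 16/41 = 39% |
| Death | 24% → 14% | 10/24 = 42% | 33% → 20% | 13/33 = 39% |

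Monte Carlo standard errors are 1.0 to 3.5 points. Protocol 12.4.1 describes choosing controls similar to cases, so the score was also fitted to case status. VE shrank again, for example 42% → 30% for PaO2/FiO2 and 36% → 24% for any severe outcome (moderate effect). With no true effect, adding PSI moved VE by at most 2 points with the vaccination score and 4 with the case score.

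For Model 4, VE fell from 43% to 25% (moderate) or 63% to 42% (stronger). If PSI also scored respiratory rate, which the visible text does not confirm, the falls would be 43% to 9% and 63% to 18%.

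*Frailty check.* Simulation B was repeated with an unmeasured frailty confounder visible only through PSI. For PaO2/FiO2, without → with PSI: no effect −18% → +10%; moderate effect 30% → 36%; stronger effect 52% → 48%.

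**The case against.** The strongest counter-argument is that PSI also carries baseline information: the protocol's list includes nursing home residency. Protocol 3 expects confounding by indication, and Protocol 9.1 names healthy-vaccinee confounding. The frailty check shows that dropping PSI can then leave VE biased downward. This stands. A reader might infer that VE is certain to be pulled toward zero; the documents do not support that, because the net direction depends on what else PSI stands for. But it argues for keeping baseline information by other means, not for matching on acute physiology. Age is already in the score, and institutional residence already feeds the risk level in SAP Appendix 2.4.

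A reader might also infer that all seven models match on components of their own outcome. The visible text shows this for oxygenation only, so for Model 3 and one limb of Model 1. Even there, PSI is a composite that counts only as far as it contributes to the fitted score.

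A third tempting reading is that the effect is largely matched away and a null result could not be interpreted. The figures show attenuation. The loss passes half only at the highest assumed correlation in Simulation A, and Simulation B keeps most of the effect for every outcome tabulated.

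Finally, the endpoint is exploratory, is pursued only if COVID-19 is frequent enough (Protocol 9.1 and 12.4.3), and SAP 5.1 applies no hypothesis test or decision rule. That limits the weight of the point but does not make PSI a confounder.

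**Conclusion.** The point holds in bounded form. By cross-reference, SAP 6.3.7.1 puts a post-vaccination severity score into the match for an outcome that is itself severity. If PCV13 acts through admission severity and the remaining covariates capture confounding, VE is attenuated: by about a quarter to 60% across the assumed correlations in Simulation A, and by about one third to two fifths with matching as the SAP describes it. These sizes rest on assumed effects and correlations, not on anything in the documents. With no true effect and no hidden confounding there is no material change. The primary VE conclusion is not touched by this point. The change should be made before the COVID-19 analysis is run.

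**What to change.** In SAP 6.3.7.1, state that the propensity score for the COVID-19 severity models omits PSI. Keep the other variables listed in SAP 6.1.1.2, including nationality and pneumonia in the last year, with exact matching on site. Add residence setting and COVID-19 vaccination, both collected under Protocol 10.3. Use the Charlson index only if restricted to conditions present before admission, since the schedule of activities (Protocol 6) and Protocol 10.5 allow it to be built from discharge codes or data entered as late as Day 180.

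The cost is a short SAP amendment with no new data. Protocol 12.4 calls for a protocol amendment only for major changes to the primary endpoint or its analysis, so none is needed here. The small downside is the loss of whatever frailty information only PSI carries; showing the result with PSI as a sensitivity analysis would make that visible.

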• To determine if the frequency of pneumococcal infection differs between hospitalised CAP patients with COVID-19 infection compared to those without COVID-19 infection, overall and stratified by age, sex, and pneumococcal risk status.	 Percentage of CAP events with pneumococcal infection identified by any means (eg, UAD, BinaxNOW[®], bacterial culture) among CAP events associated with a positive COVID-19 test compared to percentage of CAP events with pneumococcal infection identified by any means (eg, UAD, BinaxNOW[®], bacterial culture) among CAP events associated with a negative COVID-19 test, overall and stratified by age, sex, and pneumococcal risk status.
• Among the subset of hospitalised CAP patients with COVID-19 identified, to determine if the proportion who experience severe clinical outcomes (eg, ICU stay, mechanical ventilation, prolonged hospitalisation, and sequelae) differs between those with pneumococcal co-infection compared to those without pneumococcal co-infection, overall and stratified by age, sex, and pneumococcal risk status.	 Among CAP subjects with COVID-19 infection, percentage of CAP subjects with severe clinical outcomes (overall and by individual outcome) among those with pneumococcal co-infection identified by any means (eg, UAD, BinaxNOW[®], bacterial culture) compared to percentage of CAP subjects with serious clinical outcomes among those without pneumococcal co-infection identified by any means (eg, UAD, BinaxNOW[®], bacterial culture) compared to percentage of CAP subjects with serious clinical outcomes among those without pneumococcal co-infection identified by any means (eg, UAD, BinaxNOW[®], bacterial culture), overall and stratified by age, sex, and pneumococcal risk status.
• Using a test-negative design to determine the VE of PCV13 against severe COVID- 19 clinical outcomes among COVID-19 positive hospitalised CAP patients, overall and among immunocompetent persons only.	 VE calculated as minus the OR comparing the odds of having received PCV13 for cases and controls, multiplied by 100%, overall and among immunocompetent persons only, adjusted for confounders. (Cases = COVID-19-positive CAP subjects with severe clinical outcomes; Controls = COVID-19-positive CAP subjects without severe clinical outcomes).

B1851202 LOW-INTERVENTIONAL STUDY PROTOCOL

ersion 3.0, 03 February 2022	

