%	12	15%	60%	9%	1:10	170	1692	1862	1960	50%	3920	3.4
enrolled	13	15%	60%	9%	1:10	170	1692	1862	1960	30%	6533	5.7

Table 6.Sample Size Scenarios for VE Calculations At Interim

- a. Base case values are highlighted in gray; 2.5% alpha was used for all scenarios and 80% power was used for all scenarios except #11. All calculations done with OpenEpi, Version 3, open-source calculator (Sample Size-Unmatched Case Control Study; available @ https://www.openepi.com/SampleSize/SSCC.htm) and used Fleiss method with continuity correction, which is consistent with estimates based on Fischer's exact test. For these calculations, 2.5% alpha was used to split alpha allocated between interim analysis and final analysis (ie, 2.5% to each analysis).
- b. Includes projected 5% of subjects with no valid pneumococcal serotype specimen result.
- c. Number of "CAP inpatients needed" is based on the percentage of CAP patients enrolled in prior column, which accounts for loss of potential subjects who declined participation or were not offered participation due to incomplete surveillance.
- d. Estimate 1800 CAP admissions annually in the surveillance area and 36% would be immunocompromised, leaving ~1150 immunocompetent CAP admissions annually and ~104 vaccine-type pneumococcal CAP cases.

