#### 2.2. Study Design

This study is a low interventional, prospective, multicentre, hospital-based study involving adults 60 years of age and older hospitalised with CAP at participating sites. Hospital surveillance data will be used for incidence rates calculations. Vaccine effectiveness will be calculated using a TND. The approximate study duration will be 4 years.

Assuming 15% PCV13 vaccination coverage among controls, 60% VE, 9% VT serotype prevalence, a ratio of 1:10 case and controls and with alpha=0.025 and 80% power, enrolment of 170 cases and 1,692 controls would be required to allow appropriate evaluation of the study objective.

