- VE calculated as 1 minus the OR comparing the odds of having received PCV13 by cases and controls, multiplied by 100%, overall and among immunocompetent persons only, adjusted for confounders. (Cases=COVID-19-positive CAP subjects with severe clinical outcomes; Controls=COVID-19-positive CAP subjects without severe clinical outcomes. This will be a nested case-control study, and the COVID-19 status will be determined from standard-of-care viral testing. The cases are CAP patients with COVID-19 with severe clinical outcomes, and the controls are the CAP patients with COVID-19 without severe clinical outcomes. Several clinical outcomes will be used in the definition of cases and
  - Patients admitted to the ICU

controls as stated below:

- Patients with PaO2/FiO2 ratio <250 mmHg

- Patients with respiratory rate >30 breaths/min
- Patients died
- Patients received mechanical ventilation
- Patients diagnosed as ARDS
- Any severe clinical outcome mentioned above
- Frequency of pneumococcal carriage among subjects with current/recent COVID-19 infection compared to frequencyof pneumococcal carriage among subjects without current/recent COVID-19 infection, overall and stratified by age, sex, and pneumococcal risk status.
  - In this analysis, the denominator will be the Saliva Carriage Subpopulation with COVID-19 status to be determined from standard-of-care viral testing.

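### Severe COVID-19 endpoint: 1 − OR from a closed cohort is labelled VE and lies further from the null than 1 − RR unless severe outcomes are rare; separately, the borrowed matching loses participants

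*SAP*

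**What the plan says.** Protocol section 8 sets an exploratory objective of estimating PCV13 effectiveness against severe COVID-19 outcomes by a test-negative design. Its endpoint draws both groups from one population: "Cases = COVID-19-positive CAP subjects with severe clinical outcomes", with the remaining COVID-19-positive CAP participants as controls. SAP 2.1.4 keeps the test-negative wording. SAP 3.3.2 instead describes a nested case-control study and gives the measure as "VE calculated as 1 minus the OR comparing the odds of having received PCV13 by cases and controls". SAP 6.3.7 repeats it: "VE will be calculated as 1 minus the odds ratio for PCV13 vaccination among cases and controls".

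SAP 6.3.7.1 lists seven models (its lead-in counts six): any severe outcome, ICU admission, PaO2/FiO2 below 250, respiratory rate above 30, death, mechanical ventilation and ARDS. For each, "we will employ a conditional logistic regression model and will estimate odds of exposure to PCV13 among cases versus controls". Controls come from the propensity-score matching of SAP 6.1.1.2: nearest neighbour, no replacement, caliper 0.2, exact on site. On the number of controls, "The maximum number of controls for a case will be determined based on the exact case-control ratio in the data". A case with too few controls in the caliper keeps those it has. Nothing is said about a case with none, or about a ratio below one control per case. No risk ratio and no whole-cohort analysis is planned for this endpoint.

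**The concern.** In a test-negative design the controls are ill from other causes, and the odds ratio can be read as a rate ratio without assuming rare disease. Protocol 9.1 rests the design on the vaccine having no effect on those other aetiologies. That reasoning does not carry over here. The controls are the non-cases of the same closed group, identified once the outcome is known, so 1 − OR approximates the relative reduction in risk only when the outcome is rare.

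At stake is a percentage that carries the same VE label as the primary endpoint but is stretched by the choice of scale. A second, separate issue is that a matching rule written for a primary analysis with about ten controls per case is reused in a smaller subset where that ratio may be far lower.

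**Working it through.** **1. The plan's own figure.** No sample size, power or event rate is stated for this endpoint. The only sample size is for the primary VE (SAP 2.2). It takes PCV13 uptake of 15% in controls, a VE of 60%, VT serotypes in 9%, ten controls per case and an alpha of 0.025; the result is given as "and 80% power, enrolment of 170 cases and 1,692 controls would be required". Protocol 12.1.2 says the calculation "used Fleiss method with continuity correction". With OR = 0.40, coverage in cases is 0.40 × 0.15 / (1 + 0.15 × (0.40 − 1)) = 0.06 / 0.91 = 0.0659. At two-sided alpha 0.025 and 80% power the method gives 157 cases before and 170 after continuity correction, with 1,700 controls at 1:10. At a ratio of 9.95 it gives 170 and 1,691, against 1,692 stated. The figure reproduces. It shows the setting the primary analysis was sized for, and says nothing about severe COVID-19.

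**2. Inputs for this endpoint.** Groups, effect measure and matching rule are as set out in the SAP. The risk of a severe outcome in the unvaccinated, p0, is not stated; 5% to 60% is assumed. The number of COVID-19-positive CAP participants is not stated; 400 is assumed in step 6.

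**3. Scale.** OR = RR(1 − p0) / (1 − RR × p0). Example with RR 0.60 and p0 0.50: 0.60 × 0.50 / (1 − 0.30) = 0.30 / 0.70 = 0.429, so 1 − OR = 57.1%.

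| p0 (assumed) | 1 − OR, true 20% | true 30% | true 40% | true −25% |
|---|---|---|---|---|
| 5% | 20.8% | 31.1% | 41.2% | −26.7% |
| 10% | 21.7% | 32.3% | 42.6% | −28.6% |
| 30% | 26.3% | 38.0% | 48.8% | −40.0% |
| 50% | 33.3% | 46.2% | 57.1% | −66.7% |
| 60% | 38.5% | 51.7% | 62.5% | −100.0% |

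Read backwards, a reported 1 − OR of 60% is a relative risk reduction of 57.4% at p0 = 10%, 51.2% at 30% and 42.9% at 50%.

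**4. Could the outcome be common?** Any one of six criteria makes the composite (SAP 3.3.2). PaO2 is derived from SpO2 by SAP Appendix 5. PaO2/FiO2 falls below 250 at SpO2 86% on room air (52/0.21 = 248), 93% at FiO2 0.28 (69/0.28 = 246) and 97% at FiO2 0.40 (96/0.40 = 240). This locates the threshold; it does not say how many patients cross it.

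**5. Forced loss of cases.** With at least one control required per case and no replacement, if a share p > 50% is severe then at most (1 − p)/p of cases can be matched. The minimum share lost is (2p − 1)/p: 0.10/0.55 = 18% at 55% and 0.20/0.60 = 33% at 60%. At or below 50% no loss is forced, but a case with no control left in its caliper and site adds nothing to a conditional likelihood.

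**6. Simulation.** Settings: 250 runs each, N = 400, about 15% vaccinated, true RR 0.60, caliper 0.2 SD of the logit, exact site. Ranges cover a score modelled on vaccination and one modelled on case status.

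| Severe risk | Matched 1 − OR | Cases lost | Power: matched OR | Power: whole-cohort logistic | Power: whole-cohort RR |
|---|---|---|---|---|---|
| 10% | 42–44% | 2–3% | 0.02–0.05 | 0.05 | 0.01–0.02 |
| 28% | 49% | 3–9% | 0.38 | 0.46–0.48 | 0.41–0.43 |
| 47% | 58–60% | 16–28% | 0.70–0.73 | 0.84–0.88 | 0.78–0.81 |
| 55% | 62–63% | 31–42% | 0.81–0.82 | 0.96 | 0.88–0.89 |

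Whole-cohort modified Poisson returned 39–42% for the true 40% at every risk. Controls lost ranged from 14% to 41%.

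**The case against.** The best defence is that this is an exploratory endpoint, run only if COVID-19 is frequent enough (Protocol 9.1 and 12.4.3). SAP 5.1 applies no hypothesis test or decision rule, and the 1 − OR formula is stated openly. SAP 3.3.2 already says nested case-control. A matched odds ratio that declares its scale is a legitimate quantity, and no section plans to compare it with the primary VE. All of that stands and limits how much weight the point carries. It does not cure calling the result vaccine effectiveness, and the test-negative wording remains in both sets of objectives.

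A reader might also infer more than the documents support:

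- That severe outcomes are common. No frequency is given. Six of the seven models are single outcomes, and nothing shows that death, ARDS or ventilation is common. SAP 3.4 sets PaO2 to missing when the SpO2 and FiO2 timings differ, which limits entry through PaO2/FiO2.
- That VE is always overstated. The distortion is away from the null, so a negative VE becomes more negative.
- That matching necessarily discards cases. The SAP does not say so. Loss is forced only above 50% severe; otherwise it depends on whether a control is left in caliper and site.
- That the odds ratio costs precision. The loss comes from matching: whole-cohort logistic regression recovers it and has somewhat more simulated power than the risk ratio. The risk ratio corrects the scale.

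**Conclusion.** The point holds in a conditional form. The comparison is within a closed cohort, the test-negative rationale does not apply, and 1 − OR is further from the null than 1 − RR unless the outcome is rare. For a true 40% reduction the gap is about 1 to 3 percentage points at 5–10% risk, 9 at 30% and 17 at 50%. It therefore concerns mainly the composite and the PaO2/FiO2 model, and is small for any rare component.

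Matching is a distinct and lesser issue: controls are lost in general, some cases when no eligible control remains, and at least one third of cases if 60% are severe. The risks are assumed throughout, and the simulated losses and power also depend on the assumed covariate effects and N. A correction is worth making because it is cheap, not because any main conclusion of the study depends on it.

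**What to change.** In SAP 6.3.7.1, analyse all COVID-19-positive CAP participants with a non-missing outcome, without selecting controls. For the composite and each component, estimate a covariate-adjusted risk ratio for PCV13, by modified Poisson regression with robust standard errors or by standardisation from a logistic model. Report 1 − RR as the relative reduction in severe outcome among hospitalised COVID-19 CAP, alongside the severe risk by vaccination status. Remove the test-negative label from this objective in Protocol sections 3 and 8 and SAP 2.1.4, and align the endpoint wording in Protocol section 8 and SAP 3.3.2 and 6.3.7.

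If the matched analysis is kept as supplementary, label it an odds ratio, state what happens to a case without a control and when the ratio is below one, and report the unmatched cases and controls.

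The cost is SAP and exploratory-endpoint wording and one different model, with no new data. The reported effect will lie closer to the null, and no useful gain in power should be expected where the severe risk is low.
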